5.3.3 Visual Disturbances

The secondary safety endpoint is rates of severe and most bothersome visual disturbances as reported by subjects using the QUVID questionnaire at month 6. Descriptive summaries (rates and 95% (two-sided) exact confidence intervals) of severe and most bothersome visual disturbances will be presented for each IOL group and the difference between the IOL groups.

The number and percentages of subjects in each category of responses to each question on the QUVID questionnaire will be reported by IOL group at each visit this questionnaire is administered.

5.3.4 Adverse Events

The third safety endpoint is adverse events. Incidence rates observed for each IOL group will be compared to the cumulative and persistent adverse event Safety and Performance Endpoint rates in IS EN ISO 11979-7:2014. An eye with multiple ocular adverse events of the same preferred term is only counted once toward the total of this preferred term. The Safety and Performance Endpoint rate is considered not exceeded if the lower exact binomial 95% confidence limit does not exceed the Safety and Performance Endpoint rate.

The following SAS pseudo code will be used to generate the summaries above.

```
proc freq data=AE_SPE;
by SPE_AE;
tables LENS_MODEL / binomial (exact) alpha=0.05;
run;
```

The frequencies of adverse events will be presented overall, and by subcategories of age (<65 years vs. \geq 65 years) and investigative site, separately for cumulative and persistent adverse events. Additionally, frequencies and 95% (two-sided) exact confidence intervals will be reported for adverse events related to the IOL for each IOL group. Adverse events related to the IOL are referred to as adverse device effects.

Adverse events will be summarized in the following tables, by IOL group:

1. All Adverse Events (Serious and Non-Serious Combined)
 - a. Ocular
 - b. Non-Ocular
2. All Adverse Device Effects
 - a. Ocular
 - b. Non-Ocular
3. All Serious Adverse Events (including Serious Adverse Device Effects)
 - a. Ocular
 - b. Non-Ocular
4. Subject Listings
 - a. Non-Serious Ocular
 - b. Non-Serious Non-Ocular
 - c. Serious Ocular
 - d. Serious Non-Ocular

All ocular tables will be presented separately for first operative eyes and all eyes.

In addition, listings of adverse events will be provided. The listings will include the following variables: treatment, site, subject, eye, days from surgery, duration, adverse event description, causality, severity, seriousness, outcome and preferred term.

Table 5-2**Adverse Event Safety and Performance Endpoint Rates**

Adverse Event	SPE Rate (%)
Cumulative	
Cystoid Macular Oedema	3.0
Hypopyon	0.3

Endophthalmitis ^a	0.1
Lens dislocated from posterior chamber	0.1
Pupillary block	0.1
Retinal detachment	0.3
Secondary surgical intervention ^b	0.8
Persistent	
Corneal stroma oedema	0.3
Cystoid macular oedema	0.5
Iritis	0.3
Raised IOP requiring treatment	0.4

^a Endophthalmitis is defined as inflammatory reaction (sterile or infectious) involving the vitreous body.

^b Excludes posterior capsulotomies.

SPE = Safety and Performance Endpoint

SPE rates are from Table B.2 – Posterior Chamber

IOL Adverse Event Rates in IS EN ISO11979-7:2014.

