	
first and all eyes. Incidence rates observed in each treatment arm (for first operative eyes, and for all eyes) will be compared to the cumulative and persistent adverse event SPE (safety and performance endpoint) rates based on 1-sided exact binomial calculation.
 
QUVID outcomes will be summarized using standard descriptive measures.
																																										
Sample Size Justification	
Approximately 250 subjects will be bilaterally implanted with either the AcrySof IQ PanOptix IOL Model TFNT00 or the AcrySof Monofocal IOL Model SN60AT in a 1:1 ratio in order to ensure that at least 113 eligible subjects complete the study in the test group and the control group. This assumes a drop-out rate of 10%, approximately.
 
Power calculations for the effectiveness objectives are summarized in the table below:
 

	Margin	Expected Difference	Std. dev	Type I error (1-sided)	Power	

Non- Inferiority						

BCDVA (4 m)	0.1	0.0	0.18	5%	99%	

Superiority						

DCNVA (40 cm)		0.1	0.18	2.5%	98%	

DCIVA (66 cm)		0.1	0.18	2.5%	98%	

Spectacle Wear		20%		2.5%	83%	

 
All expected differences for tests of superiority favor the test lens. Estimates of VA endpoints reported in logMAR.
 
Adverse Events: For any event where a 0 incidence is observed in 113 first-operative eyes in the AcrySof IQ PanOptix IOL test group, the upper exact binomial 95% confidence limit is less than 3%. Thus, with 95% confidence, the true adverse event rate is less than 3%.
 		Margin	Expected Difference	Std. dev	Type I error (1-sided)	Power	Non- Inferiority						BCDVA (4 m)	0.1	0.0	0.18	5%	99%	Superiority						DCNVA (40 cm)		0.1	0.18	2.5%	98%	DCIVA (66 cm)		0.1	0.18	2.5%	98%	Spectacle Wear		20%		2.5%	83%
	Margin	Expected Difference	Std. dev	Type I error (1-sided)	Power																																						
Non- Inferiority																																											
BCDVA (4 m)	0.1	0.0	0.18	5%	99%																																						
Superiority																																											

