15.7.3 Analysis for Third Safety Objective

The third safety endpoint is adverse events. Incidence rates observed for each IOL group will be compared to the cumulative and persistent adverse event Safety and Performance Endpoint rates in IS EN ISO 11979-7 SPE grid rates. An eye with multiple ocular adverse events of the same preferred term is only counted once toward the total of this preferred term. The Safety and Performance Endpoint rate is considered not exceeded if the lower exact binomial 95% confidence limit does not exceed the Safety and Performance Endpoint rate.

The frequencies of adverse events will be presented overall, and by subcategories of age (<65 years vs. \geq 65 years) and investigative site, separately for cumulative and persistent adverse events. Additionally, frequencies and two-sided 95% confidence intervals will be reported for adverse events related to the IOL for each IOL group. Adverse events related to the IOL may also be referred to as adverse device effects.

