4.3.1 Primary Effectiveness Analyses

Least Squares Means (LSMEANS) from the mixed effects model chosen during the model selection step will be employed to estimate the difference in means (AcrySof IQ PanOptix IOL Model TFNT00 minus AcrySof Monofocal IOL Model SN60AT) and the associated 90% (two-sided) confidence interval for the non-inferiority test and 95% (two-sided) confidence interval for the superiority test.

The non-inferiority hypothesis (first co-primary) will be deemed supported if the upper 95% confidence limit is less than the non-inferiority margin of 0.10 logMAR.

The superiority hypothesis (second co-primary) will be deemed supported if the upper 97.5% confidence limit is less than 0.0 logMAR.

SAS pseudo code for the above models is provided below.

```
proc mixed data=visual_acuity;
  where OPERATIVE_EYE = 'First' AND VISIT='VISIT4A';
  class LENS_MODEL SITE;
  model VA = LENS_MODEL /DDFM = satterth;
  random SITE SITE*LENS_MODEL; *[OR] random SITE;
  lsmeans LENS_MODEL / pdiff cl;
  estimate 'Trt_Eff' LENS_MODEL 1 -1;
run;
```

An analysis with a mixed-effect model analysis of variance (ANOVA) accounting for correlation between the first and the second eye will be performed as a sensitivity analyses. The following SAS pseudo code will be used:

```
proc mixed data=visual_acuity;
  where VISIT='VISIT4A';
  class LENS_MODEL SITE OPERATIVE_EYE;
  model VA = LENS_MODEL /DDFM = satterth;
  random SITE SITE*LENS_MODEL; *[OR] random SITE;
  repeated OPERATIVE_EYE / subject=USUBJID(SITE) TYPE=CS;
  lsmeans LENS_MODEL / pdiff cl;
  estimate 'Trt_Eff' LENS_MODEL 1 -1;
run;
```

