5.3.1 Secondary Surgical Interventions

Descriptive summaries (count, rate and 95% (two-sided) exact confidence interval) of secondary surgical interventions will be presented for each IOL group and the difference between the groups, separately for first operative eyes and all eyes in each of the following categories:

- 1) Related to IOL - due to optical properties
- 2) Related to IOL - not due to optical properties
- 3) Unrelated to IOL
- 4) Overall

A listing of all SSIs will also be presented.

The following SAS pseudo code will be used.

```
proc freq data=SSI;
  tables LENS_MODEL*SSI / alpha=0.05;
  exact riskdiff;
  run;
```

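### The SAP 5.3.4 code for the SPE comparison tabulates lens model instead of events, and its alpha=0.05 gives a one-sided 97.5% lower limit where the text points to 95%

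*SAP*

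**What the plan says.** SAP 5.3.4 defines the comparison in prose: "Incidence rates observed for each IOL group will be compared to the cumulative and persistent adverse event Safety and Performance Endpoint rates". The rule, worded alike there and in Protocol 15.7.3, is that an SPE rate counts as not exceeded if "the lower exact binomial 95% confidence limit does not exceed the Safety and Performance Endpoint rate". Neither sentence says whether the limit is one-sided. SAP Table 5-2 lists 11 SPE rates, from 0.1% to 3.0%.

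The SAP then commits to its code: "The following SAS pseudo code will be used to generate the summaries above". The code runs BY `SPE_AE`, and its only table request is "tables LENS_MODEL / binomial (exact) alpha=0.05". The section also states: "All ocular tables will be presented separately for first operative eyes and all eyes".

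Four other places bear on how this should be read:

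- SAP 5.3.1, for secondary surgical interventions (SSI), crosses lens with event: "tables LENS_MODEL*SSI / alpha=0.05".
- The Protocol synopsis (Planned Analyses) describes the SPE comparison as "rates based on 1-sided exact binomial calculation", for first operative eyes and for all eyes, without giving a level.
- SAP 4.3.1 pairs an upper 95% limit with "the associated 90% (two-sided) confidence interval for the non-inferiority test", and an upper 97.5% limit with a two-sided 95% interval.
- SAP 7 and Protocol 15.10 state that no events in 113 first eyes give an upper exact 95% limit below 3%.

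**The concern.** There are two separate faults in one line of code.

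First, a BY statement only splits the data. The variable whose proportion is estimated is `LENS_MODEL`. Whether `SPE_AE` is an event type or an event flag, and whether the data set holds event records or all eyes, the result is the fraction of records in one lens level. The rule needs the event rate within each lens. SSI is at least tabulated by lens in SAP 5.3.1; for the other 10 SPE items this is the only code in the plan.

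Second, `alpha=0.05` requests a two-sided 95% interval, so its lower end is a one-sided 97.5% limit. If the rule means a one-sided 95% limit, the code makes it harder to declare an SPE rate exceeded, which favours the lens on a stated safety objective. A program repaired to count events but still carrying `alpha=0.05` would look correct and keep this fault.

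**Working it through.** **Inputs.** SPE rates from SAP Table 5-2. About 125 subjects per lens (SAP 1.2), hence about 125 first eyes each. 113 completers per lens (SAP 7). Event counts and true rates used below are assumptions for illustration.

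**1. The plan's own figure.** For 0 events in n eyes the upper exact limit is 1 − a^(1/n).

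- One-sided 95%: 1 − 0.05^(1/113) = 2.62%, below 3%.
- Upper end of a two-sided 95% interval: 1 − 0.025^(1/113) = 3.21%, above 3%.

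The stated figure reproduces only if the exact binomial 95% limit is one-sided. The pairing in SAP 4.3.1 follows the same convention, and the synopsis calls the SPE calculation 1-sided.

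**2. What the code returns.** Suppose cumulative cystoid macular oedema (CME, SPE 3.0%) occurs in 8 test and 2 control first eyes of 125 each.

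- Required: 8/125 = 6.4%, one-sided 95% lower limit 3.22%, exceeded; and 2/125 = 1.6%, lower limit 0.29%, not exceeded.
- Coded, event records only: 2/10 = 20% (2.5% to 55.6%), or its complement.
- Coded, one record per eye: 125/250 = 50% (43.6% to 56.4%).

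Neither coded figure is an event rate, and there is one where two are needed.

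**3. What the tail changes.** The exact lower limit for x events in N eyes is the a-quantile of Beta(x, N − x + 1), with a = 0.05 (one-sided 95%) or a = 0.025 (as coded). At N = 125:

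| Item (SPE rate) | Events | Lower limit, a = 0.05 | Lower limit, a = 0.025 |
|---|---|---|---|
| Cumulative CME (3.0%) | 8 | 3.22% | 2.80% |
| Cumulative CME (3.0%) | 9 | 3.81% | 3.35% |
| Persistent CME (0.5%) | 3 | 0.657% | 0.498% |
| Persistent CME (0.5%) | 4 | 1.10% | 0.88% |

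The smallest count that exceeds the SPE rate is therefore 8 versus 9 for cumulative CME and 3 versus 4 for persistent CME. The other nine items are unchanged, including SSI (4 under both).

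The pattern depends on N. From 119 to 124 only cumulative CME differs. The four 0.3% items (hypopyon, retinal detachment, corneal stromal oedema, iritis) differ, 2 versus 3, only at 118 or below: 2/118 gives 0.302% and 2/119 gives 0.299% at a = 0.05. The range checked was 110 to 131. For all eyes, taking 250 per lens and treating eyes as independent, 9 of 11 items differ by one event; only SSI and raised IOP do not.

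**4. Chance of flagging at N = 125.** P(X ≥ count), X ~ Bin(125, p):

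| Item | Assumed true rate | One-sided 95% | As coded |
|---|---|---|---|
| Cumulative CME | 5% | 29% | 17% |
| Cumulative CME | 6% | 48% | 34% |
| Cumulative CME | 8% | 79% | 68% |
| Persistent CME | 1.5% | 29% | 12% |
| Persistent CME | 2% | 46% | 24% |

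With the true rate exactly at the SPE rate, the chance of a false exceedance is 3.5% versus 1.3% (cumulative CME) and 2.5% versus 0.4% (persistent CME).

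**The case against.** The block is labelled pseudo code, and the prose above it gives the quantity, the counting rule and the decision rule. A statistician would program from the prose, and a 20% or 50% output set against rates of 0.1% to 3.0% would be caught. This stands, and it is why the first fault is minor. It is not a reason to leave the code, because the SAP says that code will be used.

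On the tail, the rule sentence states no sidedness. Nearby safety analyses (SSI, visual disturbances, adverse device effects) use two-sided 95% exact intervals. The synopsis gives no level, so a one-sided 2.5% test would also fit it. The convention in SAP 4.3.1 belongs to effectiveness, and the 0/113 statement concerns an upper limit. It is therefore fair that one-sided 95% is an inference. But the 0/113 statement names the same kind of limit and is true only one-sided, and where SAP 5.3.4 wants a two-sided interval, for device effects, it says so. The weight of the text is on one side.

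The effect is small: at N = 125 two of 11 items move, by one event each. The persistent CME difference rests on 0.498% against 0.5%. The Safety Analysis Set, not the 113 completers, supplies the denominator. Study success is defined on effectiveness only, and SAP 5.2 describes the safety analysis as mainly descriptive. All of this stands.

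**Conclusion.** The concern holds, at minor severity. Followed as written, the SAP 5.3.4 code cannot produce the event rate per lens that the third safety objective needs; this part is certain. The coded lower limit is one-sided 97.5%, whereas the documents taken together point to one-sided 95%; this part rests on reading the unstated sidedness from the synopsis, SAP 4.3.1 and the 0/113 figure. At the planned 125 first eyes per lens, the tail shifts the exceedance count by one event for cumulative and persistent CME and for nothing else. More items shift at 118 eyes or fewer, or in the all-eyes comparison if eyes are treated as independent. The flagging probabilities depend on assumed true rates that the documents do not supply. No effectiveness conclusion or success criterion is affected.

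**What to change.** In SAP 5.3.4, build one record per eye at risk in the Safety Analysis Set and SPE item, with EVENT = Y or N. Run it for first operative eyes (the objective), then for all eyes:

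`by LENS_MODEL SPE_AE; tables EVENT / binomial(exact level='Y') alpha=0.10;`

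The lower end of that interval is the one-sided 95% limit. Zero-event items have no Y level, so handle them explicitly: report 0/N, lower limit 0, SPE rate not exceeded. State in SAP 5.3.4 and Protocol 15.7.3 that the limit is one-sided 95%.

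The cost is a few code lines and one clarifying sentence before database lock. The sponsor should decide whether the protocol sentence counts as administrative under Protocol section 5 or needs an amendment. No endpoint, sample size or effectiveness rule changes. The downside at N = 125 is that both CME items are flagged one event earlier. With every true rate at its SPE value and items independent, the chance of at least one false exceedance per lens, 1 − ∏(1 − per-item chance) over the 11 items, rises from about 9% to 13%. Each item stays below 5% for first eyes.

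A separate tidy-up for the same revision: with default sorting of the SAP's level names, the `LENS_MODEL 1 -1` estimates in SAP 4.3.1, 4.5 and 4.6.2 give control minus test, the reverse of the stated contrast. Fix the level order or use `-1 1`.

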5.3.5 Intraocular Pressure

Intraocular pressure measurements will be recorded in mmHg and rounded to the nearest whole mmHg.

All analyses will be presented by IOL group, separately for first and second operative eyes.

Descriptive summaries (N, mean, median, standard deviation, minimum, maximum and 95% (two-sided) confidence interval) of observed values and change from baseline values will be presented at each study visit by IOL group, separately for first and second operative eyes.

A summary table with number and percentages of eyes in each category of IOP change from baseline to last on-treatment intraocular pressure assessment and to any visit by operative eye will be presented by IOL group according to the following categories: >30 mmHg increase, 21 to 30 mmHg increase, 11 to 20 mmHg increase, 6 to 10 mmHg increase, -5 mmHg decrease to 5 mmHg increase, 6 to 10 mmHg decrease, 11 to 20 mmHg decrease, 21 to 30 mmHg decrease, and >30 mmHg decrease, separately for first and second operative eyes. For change to any visit, an eye will be counted only in the category that represents maximum change from baseline across all post-baseline assessments.

A listing will be provided which presents all eyes with an increase or decrease in intraocular pressure of more than 10 mmHg at any visit compared to the same eye at baseline. The listing will include the following variables: treatment, site, subject, age, sex, visit, days from surgery, eye, baseline value, value at the visit and a change from baseline value.

5.3.6 Slit Lamp Observations

For each slit-lamp parameter, number and percentages of eyes that experience abnormality at any post-operative visit will be presented by IOL group, separately for first and second operative eyes.

A listing will be provided which presents all eyes with an abnormality in any slit-lamp parameter at any post-operative visit. The listing will include all slit-lamp data from all visits with the following variables: treatment, site, subject, age, sex, visit, eye, parameter, baseline value, and value at the visit.

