										Part 1	Part 2	
Procedure/ Assessment	Screen (Day -30 to 0)	Implant 1	Day 1-2	Day 7-14	Day 30- 60	Implant 2	Day 1-2	Day 7-14	Day 30- 60	Day 120-180 (from 2 nd eye)		N/A
for spectacle need												
Operative Eye		X				X						
Surgical Problems		X				X						
Other Procedures at Surgery		X				X						
Incision Site		X				X						
Final Incision Size		X				X						
Lens Information		X				X						
IOL Damage		X				X						
Slit Lamp Examination	X		X	X	X		X	X	X		X	X
Fundus Visualization					X				X			X
Dilated Fundus Examination	X				X				X			X
IOL Observations			X	X	X		X	X	X			X
Secondary Surgical Interventions			X	X	X		X	X	X			X
Subjective Posterior Capsule Opacification			X	X	X		X	X	X			X
Posterior Capsulotomy			X	X	X		X	X	X			X
Lens decentration and tilt			X		X			X	X			X

	Visit 0	Visit 00	Visit 1	Visit 2	Visit 3	Visit 00A	Visit 1A	Visit 2A	Visit 3A	Visit 4A*		USV
										Part 1	Part 2	
Procedure/ Assessment	Screen (Day -30 to 0)	Implant 1	Day 1-2	Day 7-14	Day 30- 60	Implant 2	Day 1-2	Day 7-14	Day 30- 60	Day 120-180 (from 2nd eye)		N/A
Intraocular pressure	X		X	X	X		X	X	X		X	X

Xb - Binocular testing is performed on the study group subjects who are implanted bilaterally with the MIOL and on the control group subjects who are implanted bilaterally with the control IOL. The questionnaires will be completed in all subjects.

[REDACTED]

[REDACTED]

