- Perform dilated fundus exam noting any issues with fundus visualization due to the lens optic. [Both Eyes, Bilateral]
- Record any AEs including SSIs.

Note: Serious adverse events (SAEs) including SSIs must be entered into EDC within 24 hours of the Investigator's knowledge. Refer to Section 13 Adverse Events and Device Deficiencies for further detail.

- Record any device deficiencies. Refer to Section 13 Adverse Events and Device Deficiencies for further detail.

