13.2 Monitoring for Adverse Events

At each visit, after the subject has had the opportunity to spontaneously mention any problems, the Investigator should inquire about AEs by asking the standard questions:

- "Have you had any health problems since your last study visit?"
- "Have there been any changes in the medicines you take since your last study visit?"

Changes in any protocol-specific parameters and/or questionnaires evaluated during the study are to be reviewed by the Investigator. Any untoward (unfavorable and unintended) change in a protocol-specific parameter or questionnaire response that is clinically relevant, in the opinion of the Investigator, is to be reported as an AE. These clinically relevant changes will be reported regardless of causality.

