13.3 Procedures for Recording and Reporting

AEs are collected from the time of informed consent. Any pre-existing medical conditions or signs/symptoms present in a subject prior to the start of the study (ie, before informed consent is signed) are not considered AEs in the study and should be recorded in the Medical History section of the eCRF.

In addition, aqueous cells and flare, corneal edema, raised IOP and superficial punctate keratitis are examples of early post-operative findings that are typically observed following ocular surgery. These are not considered AEs if they can be reasonably expected to resolve within a week and not result in any untoward long term visual outcome impact.

For each recorded event, the ADEs and SAEs documentation must include: date of occurrence, severity, treatment (if applicable), outcome, and assessments of the seriousness and causality. In addition, the Investigator must document all device deficiencies reported or observed with test and control articles on the Device Deficiency eCRF. The site must submit all available information on ADEs, SAEs, and device deficiencies to the Study Sponsor immediately as follows:

- ADEs or SAEs are documented on the *Serious Adverse Event and Adverse Device Effect* eCRF within 24 hours of the Investigator's or site's awareness.
- Device deficiencies are documented on the *Device Deficiency* eCRF within 24 hours of the Investigator's or site's awareness.

- A printed copy of the completed *Serious Adverse Event and Adverse Device Effect* and/or *Device Deficiency* eCRF must be included with product returns.
- Additional relevant information after initial reporting must be entered into the eCRF as soon as the data become available.
- Document any changes to concomitant medications on the appropriate eCRFs.
- Document all relevant information from Discharge Summary, Autopsy Report,
- Certificate of Death etc., if applicable, in narrative section of the *Serious Adverse Event and Adverse Device Effect* eCRF.
- UADEs must be reported to the IRB as soon as possible, but not later than 10 working days after the Investigator's or site's awareness.

Note: Should the EDC system become non-operational, the site must complete the appropriate paper *Serious Adverse Event and Adverse Device Effect* and/or *Device Deficiency* Form. The completed form is faxed or emailed to the Study Sponsor at

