5.1 Safety Endpoints

The safety endpoints are:

Primary Safety (6 months)

- Cumulative rate of secondary surgical interventions (SSIs) related to the optical properties of the IOL
- Binocular Distance Contrast Sensitivity
 - Photopic without glare (3, 6, 12, 18 cycles per degree)
 - Photopic with glare (3, 6, 12, 18 cycles per degree)
 - Mesopic without glare (1.5, 3, 6, 12 cycles per degree)
 - Mesopic with glare (1.5, 3, 6, 12 cycles per degree)

Secondary Safety (6 months)

- Rates of severe and most bothersome (separately) visual disturbances as reported by the subjects using a questionnaire (QUVID)

Third Safety (6 months)

- Cumulative and persistent rates of Adverse Events in first operative eyes

Other Safety

- Rates of all visual disturbances as reported by the subjects using the QUVID questionnaire at 6 months
- IOP
- Slit lamp observations
- Dilated fundus observations
- Ability to evaluate the fundus at 1 month
- Rates of ocular adverse events, including SSIs related to the optical properties for either eye
- Adverse events
- Device deficiencies
- IOL observations

- IOL position change
- Subjective PCO
- Posterior Capsulotomies
- Surgical Problems
- [REDACTED]

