5.3.7 Dilated Fundus Observations

For each dilated fundus parameter, number and percentages of eyes that experience abnormality at any post-operative visit will be presented by IOL group, separately for first and second operative eyes.

A listing will be provided which presents all eyes with abnormality in any fundus parameter at any post-operative visit. The listing will include the following variables: treatment, site, subject, age, sex, visit, days from surgery, eye, baseline value and value at the visit.

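### Slit-lamp and fundus tables count any post-operative abnormality without reference to baseline, and the slit-lamp table cannot separate cleared early findings from those present at Visit 4A

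*SAP*

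**What the plan says.** SAP 5.3.6 gives the slit-lamp summary as "number and percentages of eyes that experience abnormality at any post-operative visit will be presented by IOL group", separately for first and second operative eyes. SAP 5.3.7 has the same rule: "For each dilated fundus parameter, number and percentages of eyes that experience abnormality at any post-operative visit will be presented by IOL group". Neither section plans another table. Baseline values appear only in the eye-level listings, which cover eyes with a post-operative abnormality.

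SAP 5.3 defines baseline as the last measurement before exposure, and the schedule in Protocol section 6 places both exams at Visit 0. The information needed for a baseline condition is therefore collected, but the table rules do not use it.

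On early findings, Protocol 13.3 says that "aqueous cells and flare, corneal edema, raised IOP and superficial punctate keratitis are examples of early post-operative findings that are typically observed following ocular surgery". It adds: "These are not considered AEs if they can be reasonably expected to resolve within a week", provided no lasting visual effect is expected. Protocol 13.2 provides that an untoward change "that is clinically relevant, in the opinion of the Investigator, is to be reported as an AE".

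Neighbouring sections do more. IOP (SAP 5.3.5) gets change from baseline at each visit, IOL position (5.3.11) gets change from baseline, IOL observations (5.3.10) are shown by visit, and PCO (5.3.12) is shown both as worst case and by visit.

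**The concern.** An any-visit count with no baseline condition mixes findings that arose after implantation with findings the eye already had. In a randomised trial the second kind would be expected to balance. Here the subject selects the lens (Protocol 7.2), and these tables use the Safety Analysis Set, which keeps eyes with prior pathology; only the Best-Case set removes them. An arm difference could then reflect who chose which lens. The propensity score analysis in SAP 4.6.2 models visual acuity and does not reach these tables.

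The slit-lamp table has a second problem. It merges an eye with some flare on Day 1 that cleared within a week and an eye still abnormal at Visit 4A. Routine surgical reaction can then obscure a difference in lasting findings.

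For findings not reported as adverse events, a reader could not take from the tables a by-arm rate of new findings or, for slit lamp, the rate still present at the end of follow-up.

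**Working it through.** The plan states no figure on this point, so there is none to reproduce. The check has three parts.

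**1. Exams that collapse into one yes/no**

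- Slit lamp (Protocol section 6 and 12.2.2 to 12.2.5): Visits 1/1A (Day 1-2), 2/2A (Day 7-14), 3/3A (Day 30-60) and 4A Part 2. That is 4 scheduled post-operative exams per eye, 2 of them by Day 14.
- Dilated fundus: Visit 3/3A and, under Protocol 12.2.5, Visit 4A Part 2 ("Perform dilated fundus exam noting any issues with fundus visualization due to the lens optic"). That is 2 per eye, none before Day 30.
- As extracted, the section 6 row for "Dilated Fundus Examination" has marks only at Visits 0, 3, 3A and unscheduled visits, and SAP 5.1 lists "Ability to evaluate the fundus at 1 month". If the grid governs, there is 1 scheduled fundus exam per eye and no visit split to make. However, six other rows that 12.2.5 covers at Part 2 also lack a 4A mark: fundus visualization, IOL observations, SSIs, PCO, capsulotomy, and decentration and tilt. A fault in the text extraction is therefore likely, and I draw no conclusion from the grid. The baseline gap is the same either way.

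**2. Effect of the missing baseline condition (both tables)**

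Let p be the share of eyes in an arm with a pre-existing finding that persists, and n the share of otherwise normal eyes that develop a new one.

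- Any-visit rate = p + (1 − p)n
- Arm difference when n is equal in both arms = (p₁ − p₀)(1 − n)

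The rates below are assumptions:

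| n (both arms) | Pre-existing rates | Difference shown | True difference in new findings |
|---|---|---|---|
| 5% | 2 points apart | 0.95 × 2 = 1.9 points | 0 |
| 5% | 10 points apart | 0.95 × 10 = 9.5 points | 0 |
| 3% | 5% vs 10% | 7.85% vs 12.70%: 4.85 points | 0 |
| 3% | 5% vs 15% | 7.85% vs 17.55%: 9.7 points | 0 |

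Nearly all of any baseline imbalance passes into the table.

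**3. Effect of merging visits (slit lamp only)**

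Let e be the share of eyes in each arm with an early finding that clears, independent of lasting findings, and q the share abnormal at Visit 4A.

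- Any-visit rate = 1 − (1 − e)(1 − q)
- Arm difference shown = (1 − e)(q₁ − q₀)

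With assumed Visit 4A rates of 6% and 1% (difference 5 points, ratio 6.0):

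| e | Table shows | Difference | Share of true difference | Ratio |
|---|---|---|---|---|
| 10% | 15.4% vs 10.9% | 4.5 points | 90% | 1.41 |
| 30% | 34.2% vs 30.7% | 3.5 points | 70% | 1.11 |

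The absolute difference is diluted modestly. The ratio falls much further, because the early findings inflate both arms.

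**The case against.** The strongest reply is that what matters clinically is already tabulated elsewhere. Clinically relevant changes are adverse events, and conditions present before consent are not, so the ocular AE tables by IOL group already count new events. Persistent corneal stromal edema and iritis, the lasting counterparts of the early findings named in Protocol 13.3, each have a row in SAP Table 5-2 with an SPE rate of 0.3%. Retinal detachment and cystoid macular edema have rows as well. Entry criteria require clear media other than cataract and exclude clinically significant corneal abnormality, past or current inflammation, glaucoma, diagnosed degenerative disorders and retinal conditions judged confounding, which narrows the room for imbalance. The listings show baseline and visit values for every eye that could count as new. Finally, the imbalances in the working are assumed, and nothing in the documents suggests their size.

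Most of this stands, and it is why the point is minor. Three things survive it. First, findings below the exclusion thresholds that are not reported as AEs have no other planned by-arm rate. SAP 4.6.1 itself plans a subgroup of eyes with preoperative ocular pathology, so such eyes are expected. Second, the listings supply numerators to count by hand, but because they cover only abnormal eyes they do not give the number of eyes examined at each visit. Third, the SAP already summarises IOP, IOL position and PCO against baseline or by visit, so the request follows its own practice.

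A redacted entry in the protocol contents, between 15.7.3 and 15.8, cannot be assessed, and neither can the Manual of Procedures. Neither changes the table rules in SAP 5.3.6 and 5.3.7, which are fully visible.

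**Conclusion.** The concern holds, at minor severity. As written, both tables count unchanged pre-existing findings as post-operative abnormalities, and the slit-lamp table does not distinguish cleared early findings from those present at Visit 4A. Whether the fundus table has a similar visit problem depends on confirming the Visit 4A exam.

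The sizes in the working rest on assumed rates, on equal new-onset or early-finding rates in the two arms and, for the merged visits, on independence of early and lasting findings. They show how the rule behaves and do not forecast this trial's results. These are descriptive endpoints listed under Other Safety in SAP 5.1. No hypothesis test or success criterion depends on them.

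**What to change.** Add to SAP 5.3.6 and 5.3.7: *For each parameter, the number and percentage of eyes examined with a finding that is new since baseline (abnormal where baseline was normal) or, where the parameter is graded, worse than baseline will be presented at each scheduled visit where the exam is done, by IOL group, separately for first and second operative eyes.*

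- **Slit lamp:** Visits 1/1A, 2/2A, 3/3A and 4A.
- **Fundus:** Visits 3/3A, plus 4A under Protocol 12.2.5 once the schedule is confirmed.
- **Grading:** in the visible text only cells and flare are graded (SUN). Use new-since-baseline for parameters without a grade.
- **Any-visit count:** keep it as supplementary.

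The cost is SAP wording and longer descriptive tables: 4 slit-lamp visit columns and 1 or 2 fundus visit columns. No new data are needed, since the planned listings already draw on visit, baseline value and value at the visit. The Visit 4A fundus exam needs a one-line check against the original schedule.
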